7.3.3 Secondary outcome analysis

All secondary outcome analysis will be performed on PLWHIV with COVID-19 compared to HIV uninfected individuals with COVID-19.

The proportion of hospitalised patients for COVID-19, the length of stay in hospital, the length of stay on ICU, the length of extracorporeal membrane oxygenation (ECMO), and the proportion of participants with a need for kidney replacement therapy will be estimated using the Kaplan-Meier estimate. Unadjusted and adjusted hazard ratios (HR) will be estimated using the Cox proportional hazard model to assess the impact of HIV-infection on the severity of COVID-19. The adjusted variables will be the same as those used for the first primary outcome analysis.

The number of ventilator-free days (VFDs) will be compared between groups using competing risk regression, with extubation and mortality a competing event, adjusted for potential confounders.

Linear regression models will be used to compare Charlson Comorbidity Index (CCI), the age-adjusted CCI (ACCI), 30-day mortality index after COVID infection, inflammatory marker and blood cell counts at COVID-19 diagnosis between the 2 groups, adjusted for potential confounders. The sample size will be quite large to consider CCI, 30-day mortality index, inflammatory marker and blood cell counts as normally distributed variables.

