3.4 Secondary endpoints/outcomes

1. Hospitalisation for COVID-19
2. Length of stay in hospital
3. Length of stay on ICU
4. Number of ventilator-free days (VFDs)
5. Length of extracorporeal membrane oxygenation (ECMO)
6. Need for kidney replacement therapy
7. Measurement of total comorbidity burden using the Charlson Comorbidity Index (CCI) and age-adjusted CCI (ACCI)
8. Estimate risk of 30-day mortality after COVID-19 infection using pre-COVID health status (estimated using the Veterans Health Administration COVID-19 (VACO) index)
9. Inflammatory marker and blood cell counts at COVID-19 diagnosis

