4.1 Study Schema

[figure not shown]

Figure 1: Study design with cases (PLWHIV & COVID-19) and two matched control groups.

In total, 500 cases and up to 2500 controls will be analysed.

Only real-world retrospective data will be used for this study. Deidentified retrospective data will be transcribed into the eCRF system from source data at each clinical site or from existing COVID-19 cohort databases, where appropriate.

For comparing PLWHIV & COVID-19 versus HIV seronegative COVID-19 patients, a 1:1 and 1:3 matching will be performed according to the following criteria:

- Age (+/- 5 years)
- Sex
- Ethnicity (where available)
- Month of COVID-19 diagnosis (+/- 2 months)
- COVID-19 diagnosis inpatient, 1:1 matching
OR
- COVID-19 diagnosis outpatient (ambulatory), 1:3 matching

For comparing PLWHIV & COVID-19 versus PLWHIV without COVID-19, a 1:2 matching for similar risk of acquiring COVID-19 will be performed according to the following criteria:

- Age (+/- 5 years)
- Sex
- Ethnicity (where available)

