6.2 Data collection

Only real-world retrospective data will be used for this study. Deidentified retrospective data will be transcribed into the eCRF system from source data at each clinical site or from existing COVID-19 cohort databases, where appropriate. No personal identifiable data will be transmitted to NEAT ID. The data elements will be transcribed from source data according to the data collection list below. Mechanisms to ensure data quality and integrity will be deployed as per applicable standard operating procedures and in line with GCP and GPP. Patients and controls will be identified and documented by participating sites, provided unbiased matching for inpatient/outpatient status at the time of COVID-19 diagnosis is ensured. Alternatively, and to avoid potential site-related bias during selection of HIV negative controls with COVID-19 diagnosed in hospital, data from matched controls will be obtained from appropriate existing COVID-19 cohort databases, e.g. LEOSS (Lean European Open Survey on SARS-CoV-2 infected patients) or ISARIC (International Severe Acute Respiratory and emerging Infection Consortium).

For all patients the following information will be collected:

- Age
- Sex
- Ethnicity (where available)
- Comorbidities (see appendix 1)
- Weight (kg) and height (m) (to calculate BMI)

For patients with COVID-19 the following information will be collected (where applicable):

- Date of positive PCR test result (documented or patient-reported)
- COVID-19 diagnosis inpatient or outpatient
- All-cause mortality in hospital, or palliative discharge, or mortality at 6 weeks after diagnosis of COVID-19 or at discharge from hospital
- Hospitalisation for COVID-19 and length of hospitalisation
- Critical care admission (high dependency unit or intensive care unit) for COVID-19 and length of stay in critical care
- Length of invasive ventilation
- Length of extracorporeal membrane oxygenation (ECMO)
- Need for kidney replacement therapy
- Inflammatory markers and blood cell counts at COVID-19 diagnosis¹ (if available):
 - Full blood cell count (Platelet count, RBC Count, WBC count (absolute), Haemoglobin, Haematocrit, MCV, MCH, Neutrophils, Lymphocytes, Monocytes, Eosinophils, and Basophils), ALT, AST, total bilirubin, urea, serum creatinine, calcium, glucose and HbA1C levels, total cholesterol, triglycerides, CRP, D-dimer, ferritin, and lactate dehydrogenase

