7 STATISTICS AND DATA ANALYSIS

7.1 Sample size calculation

The US Veterans Ageing Cohort Study (VACS) reported at AIDS 2020 [20] that the estimated proportion of non-HIV-infected individuals hospitalized with COVID-19 was 35%, 15% in ICU, 8% with invasive mechanical ventilation and 11% died. We anticipate a 1.1 to 2-fold increase in hazard rate in PLWHIV & COVID-19 (cases) relative to HIV-negative & COVID-19 (controls). With 500 cases and 1500 controls, a two-sided log-rank test at an alpha level of 0.05 will achieve at least 80% power to detect a 1.3-fold increase in the hazard rate of hospitalization, 1.4 for ICU, 1.6 for invasive mechanical ventilation and 1.5 for death (refer to Table 1 below). The power calculation was made using the statistical software package nQuery Advanced, with the two samples Log-Rank test module (Version 8.6.1.0).

Table 1

¹ Most recent available after positive SARS-CoV-2 PCR test, up to 10 days after positive test

		Cases (PLWHIV & COVID-19, N=500); Controls (HIV-negative & COVID-19, N=up to 1500) Alpha=5% (two-sided)										
Severity outcome	Outcome (%)	Power (%)										
Hazard Risk		1.1	1.2	1.3	1.4	1.5	1.6	1.7	1.8	1.9	2.0	
Hospitalization	35	20	60	90	99	>99	>99	>99	>99	>99	>99	
ICU	15	11	31	58	81	94	99	>99	>99	>99	>99	
Invasive mechanical ventilation	8	8	19	35	54	73	86	94	98	99	>99	
Death	11	9	24	46	68	85	95	98	>99	>99	>99	

For the search for factors associated with SARS-CoV-2 infection in PLWHIV, the recommended rule of thumb for sample size estimation for multivariable logistic regression models was $n = 100 + 50i$ where i refers to number of independent variables in the final model [34]. With 1500 PLWHIV (500 with COVID-19 and 1500 controls without COVID-19), we would be able to study 28 parameters with sufficient power to produce statistics that are nearly representative of the true values in the targeted population. However, sample size less than 1500 may be sufficient for associations that yield medium to large effect size.

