7.3.2 Primary outcome analysis

The first primary outcome analysis will be performed on PLWHIV with COVID-19 versus HIV uninfected individuals with COVID-19. The endpoint is the occurrence of critical care admission (high dependency unit or intensive care unit), mortality in hospital or palliative discharge when discharged from hospital, or mortality at 6 weeks after diagnosis of COVID-19 or at discharge from hospital (where applicable). Kaplan-Meier estimates will be used to estimate the proportion of participants with the primary endpoint events. Unadjusted and adjusted hazard ratios (HR) will be estimated using the Cox proportional hazard model to assess the impact of HIV-infection on the severity of COVID-19. The validity of the proportionality assumption will be assessed and tested. The adjusted variables will be the following (potential confounders): Age (<60 vs 60-64 vs 65-69 vs 70-74 vs ≥75 years); Sex at birth (female vs male); Obesity (BMI>30 kg/m²); and Comorbidities (see appendix 1).

The second primary outcome analysis will be performed within the group of PLWHIV (PLWHIV with COVID-19 versus PLWHIV without COVID-19). The endpoint is to assess factors associated with severe COVID-19 within the group of PLWHIV. Conditional logistic regression models will be used to account for the case-control matching. The following variables will be assessed: Age (<60 vs 60-64 vs 65-69 vs 70-74 vs ≥75 years); Sex at birth (female vs male); Obesity (BMI >30 kg/m²); Comorbidities (see appendix 1); time since HIV diagnosis (years); current ART; CDC disease stage; CD4 cell nadir; last CD4 cell count/HIV-RNA before COVID-19 diagnosis (including CD4% and CD4/CD8 ratio) at baseline. For continuous variables, the decision to treat the variable as a continuous or categorical variable (as tertile) will be based on the lowest Akaike information criterion value for the corresponding univariable conditional logistic regression analysis. Variables achieving P < 0.20 in the univariable analysis will be retained for the multivariable analysis.

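### Hospitalisation is compared by HIV status after controls are matched 1:1 (inpatient) or 1:3 (outpatient) on diagnosis setting, with no stratification; Table 1's 90% power ignores that matching

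*Combined protocol and SAP*

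**What the plan says.** Section 4.1 sets two control ratios for the HIV-negative COVID-19 group, according to where the case was diagnosed: "COVID-19 diagnosis inpatient, 1:1 matching" and "COVID-19 diagnosis outpatient (ambulatory), 1:3 matching". Section 6.2 lets sites select controls "provided unbiased matching for inpatient/outpatient status at the time of COVID-19 diagnosis is ensured".

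The first secondary endpoint in section 3.4 is "Hospitalisation for COVID-19". Section 7.3.3 lists it first among the outcomes to be estimated by Kaplan-Meier ("The proportion of hospitalised patients for COVID-19, the length of stay in hospital") and compares it between the same two groups with unadjusted and adjusted Cox models. For the covariates it says: "The adjusted variables will be the same as those used for the first primary outcome analysis". In section 7.3.2 those are age band, sex, obesity and the Appendix 1 comorbidities. Diagnosis setting, matched set, strata and weights are not mentioned. Sections 7.3 and 7.3.2 do name a conditional model that respects the matching, but only for the analysis within PLWHIV.

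On power, section 7.1 states: "With 500 cases and 1500 controls, a two-sided log-rank test at an alpha level of 0.05 will achieve at least 80% power". For hospitalisation, that claim is made at a hazard ratio of 1.3. The hospitalisation row of Table 1 uses 35% hospitalised and gives 90% at 1.3.

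**The concern.** Setting at diagnosis is close to the outcome: most patients who are inpatients when diagnosed will count as hospitalised. Matching on it has two consequences.

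First, the ratios differ by setting. Each inpatient case brings one control and each outpatient case brings three. When the sets are pooled, the inpatient share is lower among controls than among cases by construction. Adjusting for age, sex, obesity and comorbidities does not undo a sampling ratio fixed by setting, and the Kaplan-Meier proportions and unadjusted hazard ratio are not adjusted at all. The false excess points towards harm from HIV, which is the study's hypothesis, and it can be as large as the 1.1 to 2-fold effect that section 7.1 anticipates.

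Second, stratifying to remove the bias leaves the inpatient sets with nothing to say about admission, since both members are in hospital at time zero. Only later admission after outpatient diagnosis can be compared, and Table 1 was not calculated for that smaller question.

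**Working it through.** **Inputs from the documents.** 500 cases and up to 1,500 controls; two-sided alpha 0.05; log-rank test; 35% of HIV-negative patients hospitalised; hazard ratio 1.3; stated power 90% (all section 7.1). Ratios 1:1 and 1:3 (section 4.1). Dashboard hospitalisation 436/1,187 = 36.7% (section 6.1).

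**Assumptions.** The share *s* of admissions already inpatient at diagnosis is not given and is varied from 0 to 100%. Inpatient diagnosis counts as hospitalised at time zero. The 1:1 and 1:3 ratios are fully achieved.

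**1. Reproducing Table 1.** Freedman's formula with k = 500/1,500:

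power = Φ( √(E·k) × (HR − 1)/(1 + k·HR) − 1.96 )

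Events E = 500 × (1 − 0.65^1.3) + 1,500 × 0.35 = 739. Then √(739.4/3) × 0.3/1.433 − 1.96 = 1.33, giving 90.8%. At hazard ratios 1.1, 1.2 and 1.4 the formula gives 20, 60 and 99%, as in the table. The row is therefore an ordinary unmatched two-sample log-rank calculation.

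**2. Apparent effect when HIV has none.** Let T = 0.35 in both groups, f = T·s (share of cases inpatient at diagnosis) and q = (T − f)/(1 − f) (later admission among outpatients).

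- Controls obtained = 500f + 1,500(1 − f)
- Control proportion hospitalised = [f + 3(1 − f)q] / [f + 3(1 − f)]
- Null risk ratio = T / control proportion

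Example, s = 50%: f = 0.175 and q = 0.212. Controls are 87.5 + 1,237.5 = 1,325, of whom 87.5 + 262.5 = 350 are hospitalised. That is 26.4% against 35% of cases, a ratio of 1.32.

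**3. Power in outpatient-diagnosed sets.** The same Freedman formula, with 500(1 − f) cases, 1,500(1 − f) controls and control risk q. Example, s = 50%: E = 412.5 × (1 − 0.788^1.3) + 1,237.5 × 0.212 = 372. Then √(372.4/3) × 0.3/1.433 − 1.96 = 0.37, giving 64.5%.

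| Share *s* | Controls obtained | Controls hospitalised under null | Null risk ratio | Pooled test rejects true null | Power at HR 1.3, outpatient sets (formula) | Same, set-stratified simulation |
|---|---|---|---|---|---|---|
| 0% | 1,500 | 35.0% | 1.00 | 5.1% | 90.8% | 86.3% |
| 25% | 1,412 | 31.0% | 1.13 | 50.0% | 81.3% | 76.6% |
| 50% | 1,325 | 26.4% | 1.32 | 99.8% | 64.5% | 61.0% |
| 75% | 1,238 | 21.2% | 1.65 | 100% | 37.9% | 36.7% |
| 90% | 1,185 | 17.7% | 1.98 | 100% | 18.1% | 18.7% |
| 100% | 1,150 | 15.2% | 2.30 | 100% | no information | no information |

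Null rejection rates come from 2,000 simulated studies per row and simulated power from 4,000. Solving the formula for 80% power gives s of about 28%.

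**4. Does stratifying cure it?** In outpatient-diagnosed sets stratified by matched set, the test rejects a true null in 5.0, 5.8, 5.2, 4.5 and 5.3% of studies for s = 0 to 90%. A separate Cox simulation (100 runs, no HIV effect) gave unstratified hazard ratios of 1.58 and 2.12 with 20% and 30% of cases inpatient at diagnosis. Stratified by setting, they were 1.00 and 0.98.

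**5. Sensitivity.** If only two controls per outpatient case are found, the null ratio runs from 1.0 to 1.65. With T = 36.7% it runs from 1.0 to 2.27, and power from 92% at s = 0 to 19% at s = 90%.

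**The case against.** The strongest reply is that the bias depends on a coding rule that the plan never states. If patients already in hospital at diagnosis are treated as not at risk, the pooled analysis shrinks to the 1:3 outpatient sets and the false positive rate is about 5%. That is correct arithmetic, but it is not what the plan describes. Section 7.4 puts every eligible matched subject in the analysis, and section 7.3.3 estimates the proportion hospitalised, which would lose its meaning with inpatients removed. It would also turn the endpoint into later admission without saying so.

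Four further points stand as limits:

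- Inpatient diagnosis is not identical to hospitalisation for COVID-19. Someone diagnosed during a stay for another reason may not count, so inpatient sets carry little information rather than strictly none.
- The ratios are crude; the covariate-adjusted bias has not been quantified.
- The control count is given as a ceiling in the synopsis and the Table 1 header. The shortfall alone costs little: 500 v 1,150 in the unmatched formula still gives 88.1%. The power is lost because inpatient sets drop out.
- The 35% applies to both groups only under the null. At a hazard ratio of 1.3 it is the HIV-negative figure, and the implied case totals are about 43, 41, 40, 37 and 36% for s = 0 to 90%.

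Stratifying by setting alone also removes the ratio bias. Stratifying by matched set is the closer match to the design, at some cost in power (86% v 91% at s = 0).

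**Conclusion.** The concern holds. As written, the first-listed secondary comparison is biased towards a harmful HIV association whenever cases include both inpatient and outpatient diagnoses, which is the situation the two-ratio rule provides for. The bias vanishes only if no case, or every case, is an inpatient at diagnosis. At a share of just 25% the crude null ratio is 1.13, and about half of studies with no HIV effect would be declared positive.

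The hospitalisation row of Table 1 is correct for an unmatched sample that the matching does not produce. For the comparison the design can support, the claim of at least 80% power at 1.3 fails once roughly 28% or more of admissions are inpatient at diagnosis. These sizes rest on the time-zero coding, on 35% hospitalised and on full 1:3 matching. Because the inpatient share is unknown, they should be read as a range.

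This point covers one secondary endpoint and its power row. The first primary analysis uses the same unstratified model, and its effect there was not quantified. The change should be made before analysis.

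**What to change.** - **Sections 3.4 and 7.3.3:** redefine the comparative endpoint as COVID-19 admission after an outpatient diagnosis, with the time origin and risk set stated. Restrict it to outpatient-diagnosed sets and fit a Cox model stratified by matched set. Report hospitalisation in all subjects descriptively, by diagnosis setting.
- **Section 7.1:** restate the hospitalisation row of Table 1, and the sentence on 80% power at 1.3, for that subset, as a range over stated inpatient shares.
- **Limitation:** state that overall hospitalisation by HIV status cannot be estimated from this design.

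The cost is SAP wording, one power row and its sentence. Section 6.2 already collects diagnosis setting and hospitalisation as separate items. The price is a less favourable stated power, and inpatient-diagnosed sets no longer contribute to this endpoint.

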6 STUDY PROCEDURES

6.1 Subject Identification

Most PLWHIV will be identified from sites in the NEAT ID network. PLWHIV are routinely followed-up at specialised outpatient clinics with regular follow up visits as standard of care.

Since March 2020, more than 50 European sites have registered and started to provide basic information about the number of PLWHIV with COVID-19 and disease outcomes at their centres (<https://www.NEAT-ID.org/>). The dashboard provides a first estimate about the total numbers of PLWHIV with COVID-19 and where these patients are in continued care. As of 26th April 2021, 1,187 PLWHIV with COVID-19 were reported in care across Europe, with 436 hospitalisations and 78 deaths from an estimated number of 85,279 PLWHIV in routine care at these sites. These case numbers strongly suggest feasibility to recruit sufficient numbers of PLWHIV with COVID-19 and that patients have been identified at their centres already.

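### Section 7.3.3 analyses hospital stay, ICU stay, ECMO duration and kidney replacement by Kaplan-Meier and Cox without defining the event or the role of death

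*Combined protocol and SAP*

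**What the plan says.** Section 7.3.3 puts several secondary outcomes under one method. It names "the length of stay in hospital, the length of stay on ICU, the length of extracorporeal membrane oxygenation (ECMO" and then says that these and "the proportion of participants with a need for kidney replacement therapy will be estimated using the Kaplan-Meier estimate". For the group comparison, it states: "Unadjusted and adjusted hazard ratios (HR) will be estimated using the Cox proportional hazard model to assess the impact of HIV-infection on the severity" (meaning how severe the COVID-19 illness is). The section does not say whether the event is any exit or exit alive, what is censored, or how a death during the episode is treated.

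The next paragraph handles ventilator-free days differently: they "will be compared between groups using competing risk regression, with extubation and mortality a competing event, adjusted for potential confounders".

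No other section supplies the missing rule. Section 7.3 names the time-to-event methods in general terms. Section 7.3.2 covers the primary analyses, section 7.4 defines the population, and section 7.5 covers imputation of missing values only. Section 6.2 does collect deaths: "All-cause mortality in hospital, or palliative discharge, or mortality at 6 weeks after diagnosis of COVID-19 or at discharge from hospital". It also collects the lengths of hospital stay, critical-care stay and ECMO.

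**The concern.** A hospital, ICU or ECMO episode can end in recovery or in death. Kaplan-Meier and Cox need a rule for the deaths, and the two usual rules answer different questions.

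- **Death counted as the end of the stay.** A patient who dies on day 5 contributes the same as one who goes home on day 5. A group with more deaths then seems to leave faster.
- **Death censored.** One minus Kaplan-Meier then estimates discharge as if those who died could still go home later. It overstates the proportion discharged alive and distorts any median stay read from the curve. For kidney replacement, where death prevents the event, it overstates the proportion in need.

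Section 3 hypothesises worse outcomes with HIV, and section 7.1 anticipates hazard ratios of 1.1 to 2. A mortality difference between the groups is therefore what the study expects. If the rule is not fixed in advance, it will be chosen after the data are seen, and the choice affects what the duration results appear to say about severity.

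**Working it through.** **The plan's own figures.** The documents give no figure for length of stay, ECMO duration or kidney replacement, so there is none to reproduce. The nearest figures are the log-rank powers in Table 1 of section 7.1. They reproduce with Freedman's formula, Φ(√(E·r)·(HR−1)/(1+r·HR) − 1.96), with r = 500/1500 and E = 1500p + 500(1−(1−p)^HR). The results are 90.8% for hospitalisation at HR 1.3 (stated 90), 81.2% for ICU at 1.4 (stated 81), 86.2% for ventilation at 1.6 (stated 86) and 85.4% for death at 1.5 (stated 85). Table 1 is not at issue here.

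**Inputs for the illustration**

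- Section 6.1, dashboard of people with HIV: "with 436 hospitalisations and 78 deaths from an estimated number of 85,279 PLWHIV in routine care at these sites". Deaths per hospitalisation: 78/436 = 17.9%.
- Section 7.1, HIV-negative planning rates: "hospitalized with COVID-19 was 35%, 15% in ICU, 8% with invasive mechanical ventilation and 11% died". Deaths per hospitalisation: 11/35 = 31.4%.
- Section 7.1: anticipated hazard ratio 1.1 to 2.
- Assumptions: constant hazards; the same live-discharge hazard λ in both groups; all deaths in hospital. The last makes both shares upper values. They come from unrelated sources and serve only as a low and a high value of f, the in-hospital death share in the reference group.

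**(a) Death counted as end of stay.** The reference death hazard is μ = λf/(1−f), so the total exit hazard is λ/(1−f). In the comparison group it is λ + HR·μ. The ratio is (1−f) + f·HR = 1 + f(HR−1), and λ cancels.

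| Death HR | f = 17.9% | f = 31.4% |
|---|---|---|
| 1.1 | 1.02 | 1.03 |
| 1.5 | 1.09 | 1.16 |
| 2.0 | 1.18 | 1.31 |

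The true hazard ratio for live discharge is 1 in every cell.

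**(b) Death censored.** One minus Kaplan-Meier is 1 − exp(−λt) in both groups. The true cumulative incidence of live discharge is λ/(λ+μ)·[1 − exp(−(λ+μ)t)], with HR·μ in place of μ in the comparison group. Taking λ = 0.1/day (assumed) and death HR 2:

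| Quantity | f = 17.9% | f = 31.4% |
|---|---|---|
| 1−KM at day 14, both groups | 75.3% | 75.3% |
| True at day 14, reference | 67.2% | 59.7% |
| True at day 14, comparison | 60.3% | 48.6% |
| 1−KM in the long run, both groups | 100% | 100% |
| True in the long run, reference (1−f) | 82% | 69% |
| True in the long run, comparison | 70% | 52% |

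The two Kaplan-Meier curves coincide while the true probabilities of leaving alive differ by 7 to 11 percentage points at day 14.

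**Kidney replacement, ICU and ECMO.** The direction of the error is the same wherever death precedes the event or ends the episode. The documents give no rates from which to size it.

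**The case against.** The best reply is that section 7.3.3 is incomplete, not wrong. Four parts of it deserve weight.

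- **Cox with deaths censored is a standard cause-specific analysis.** This stands. A reader might infer that the planned hazard ratio would be biased or reversed under censoring. It would not be: in the illustration it equals 1, which is the true ratio of live-discharge hazards. The fault under censoring lies in the Kaplan-Meier proportions and medians, and in reading that ratio as an effect on length of stay.
- **Total stay regardless of outcome is a legitimate measure of resource use.** This also stands, if it is declared. But the plan says these hazard ratios are to assess severity, and for that purpose a stay shortened by death misleads.
- **The size depends on the death hazard ratio.** It does. At 1.1 the artefact is only 1.02 to 1.03. A reader might instead set 31% against 18% as the two groups' death shares and obtain 0.82/0.69 = 1.19. The documents do not support that contrast. The 31% is from HIV-negative patients and the 18% from people with HIV, so by source it points away from the study's hypothesis. It also implies a death hazard ratio of (0.31/0.69)/(0.18/0.82) = 2.05, just above the anticipated range.
- **The plan commits to neither rule.** True, so one cannot say which error would occur. Keeping deaths in the risk set to the end of follow-up would also handle them, but that is not stated either. The plan does name a method, and its words "with extubation and mortality a competing event" for ventilator-free days show that the issue was recognised one paragraph later.

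**Conclusion.** The point holds as a gap in specification with a real consequence for secondary outcomes. The section applies Kaplan-Meier and Cox to three durations and to kidney replacement with no event definition and no role for death, although death is not rare on the documents' own figures (up to about 18% or 31% of hospitalisations).

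Counting death as exit gives a spurious hazard ratio of about 1.02 to 1.31. Censoring it sends the estimated proportion discharged alive towards 100%, against about 69% to 82% in the reference group. These sizes rest on constant hazards, equal live-discharge hazards and all deaths occurring in hospital. They illustrate the range and do not forecast the difference between groups.

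A reader might go on to doubt the main result. The documents do not support that: the primary composite in section 3.3 includes death, so this point leaves it unaffected. The change should be made, but it concerns secondary analyses only.

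**What to change.** Amend section 7.3.3 as follows.

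1. Define the event as leaving hospital alive, leaving ICU alive, or coming off ECMO alive, with death as a competing event.
2. Replace one minus Kaplan-Meier with Aalen-Johansen cumulative incidence.
3. Report the cause-specific Cox hazard ratio for live exit together with a Fine-Gray model or the cause-specific model for death, so that it is not read alone as an effect on duration.
4. Treat death as competing for kidney replacement.
5. State how palliative discharge counts: as live exit, with death, or as its own category.
6. If total stay regardless of outcome is also wanted as resource use, name it as a separate quantity.

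The cost is SAP wording, standard software and a little more analysis. Section 6.2 already collects in-hospital death and the durations, provided that the components of the mortality item can be separated. It does not list vital status at the end of an ICU or ECMO episode. That may have to be derived or queried, including in external cohort databases, with the analysis limited to records where it is available. Section 6.2 also lists need for kidney replacement without a date, which any time-to-event analysis of it requires, as now planned or as revised.

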3.2 Secondary objectives

1. To describe differences in the clinical manifestation of COVID-19 in PLWHIV as compared to HIV seronegative controls.
2. Describe, where appropriate, the response to treatment, including supportive care and novel therapeutics against COVID-19, including antiviral and immunomodulatory therapies
3. To describe the co-morbidities in PLWHIV and controls with COVID-19
4. To compare the COVID-19 severity in PLWHIV and controls at diagnosis and hospital admission.

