5.1 Inclusion Criteria

- Cases (PLWHIV + COVID-19)
 - Any gender
 - At least 18 years of age
 - Documented HIV-1 infection
 - Confirmed SARS-CoV-2 infection by documented, or patient-reported, positive result on PCR testing of a nasopharyngeal or respiratory sample, before 1st April 2021

Each case should be matched to a control (1:1 or 1:3 respectively for COVID-19 controls and 1:2 for PLWHIV controls) according to the matching criteria set out in section 4.1.

- Controls (COVID-19)
 - Any gender
 - At least 18 years of age
 - No documented HIV-1 infection
 - Confirmed SARS-CoV-2 infection by documented, or patient-reported, positive result on PCR testing of a nasopharyngeal or respiratory sample, before 1st April 2021
 - Meet the matching criteria
- Controls (PLWHIV)
 - Any gender
 - At least 18 years of age

- Documented HIV-1 infection
- No evidence of SARS-CoV-2 infection
- Meet the matching criteria

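### The CCI and ACCI comparison by HIV status appears to count AIDS, an item HIV-negative controls cannot score, so part of any difference is built in

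*Combined protocol and SAP*

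**What the plan says.** Secondary endpoint 7 in section 3.4 is "Measurement of total comorbidity burden using the Charlson Comorbidity Index (CCI) and age-adjusted CCI (ACCI"). No modified version of either index is named. The related secondary objective in section 3.2 is descriptive: "To describe the co-morbidities in PLWHIV and controls with COVID-19".

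The comparison itself is set in section 7.3.3, which first fixes the groups: "All secondary outcome analysis will be performed on PLWHIV with COVID-19 compared to HIV uninfected individuals with COVID-19". It then plans: "Linear regression models will be used to compare Charlson Comorbidity Index (CCI), the age-adjusted CCI (ACCI"), together with other continuous measures, "between the 2 groups, adjusted for potential confounders". It does not list those confounders. The only list given under that label is in section 7.3.2: age band, sex, obesity and the Appendix 1 comorbidities.

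Section 6.2 collects "Comorbidities (see appendix 1") for all patients. The last item of Appendix 1 is AIDS, with no definition. Section 5.1 requires "Documented HIV-1 infection" of cases and "No documented HIV-1 infection" of COVID-19 controls. The document nowhere removes AIDS from the indices, gives their item weights, or plans a version without AIDS.

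**The concern.** A comorbidity index compared between two groups should be able to take the same values in both. Here one component is closed to one group by the eligibility criteria. If that component is scored, the difference in means mixes two things: any real difference in other chronic disease, and the share of cases whose HIV disease has been classed as AIDS. The second part can only push the mean for people with HIV upwards. Matching on age, sex, ethnicity, month and place of diagnosis does not remove it.

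At stake is the reading of the result. From the planned coefficient alone, a reader could not tell whether a higher index in people with HIV reflects more cardiovascular, pulmonary or metabolic disease, or simply the way the groups were defined.

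**Working it through.** The plan gives no effect size, SD or power for CCI or ACCI, so there is no figure of its own to reproduce.

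**Inputs from the document.** 500 cases and up to 1,500 HIV-negative controls; two-sided alpha of 0.05 (section 7.1, stated there for the log-rank calculation only). AIDS item equal to zero in controls (section 5.1).

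**Assumed inputs, not in the document.** Weight of the AIDS item, w = 1 to 6. Share of cases with AIDS, p = 5% to 30%. SD of the rest of the index = 2, with 1.5 and 3 as alternatives.

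**Step 1: the built-in gap.** Suppose all other comorbidities have the same distribution in both groups. The item then contributes w × p to the case mean and 0 to the control mean, so the expected difference is w × p. The extremes are 1 × 0.05 = 0.05 and 6 × 0.30 = 1.8 points.

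**Step 2: precision.** SE = 2 × √(1/500 + 1/1,500) = 0.103. The difference detectable with 80% power is (1.960 + 0.842) × 0.103 = 0.29 points (0.22 at SD 1.5; 0.43 at SD 3).

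**Step 3: chance that the gap alone gives p < 0.05.** The item also adds variance in cases, so SE = √[(SD² + w²p(1−p))/500 + SD²/1,500], and the chance is Φ(wp/SE − 1.96). Example with w = 6, p = 10%: SE = √(7.24/500 + 4/1,500) = 0.131; 0.6/0.131 = 4.58; Φ(2.62) = 99.6%.

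Gap in points, with that chance at SD 2:

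| Weight | p = 5% | p = 10% | p = 20% | p = 30% |
|---|---|---|---|---|
| 1 | 0.05 (7%) | 0.10 (16%) | 0.20 (48%) | 0.30 (81%) |
| 2 | 0.10 (16%) | 0.20 (47%) | 0.40 (95.5%) | 0.60 (>99%) |
| 4 | 0.20 (44%) | 0.40 (93%) | 0.80 (>99%) | 1.20 (>99%) |
| 6 | 0.30 (71.5%) | 0.60 (99.6%) | 1.20 (>99%) | 1.80 (>99%) |

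The SD matters: at w = 1 and p = 20% the chance is 71% with SD 1.5 and 25% with SD 3. The control number is a ceiling, since 3 × 500 = 1,500 requires every case to be matched 1:3, while inpatient cases are matched 1:1. Fewer controls would widen the SE but leave the gap unchanged.

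**Step 4: what adjustment would do.** There are two readings of the unlisted confounders.

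- If they are the section 7.3.2 list, the AIDS covariate absorbs the gap. However, the index is a weighted sum of its items, so adjusting for those items removes nearly all of its variation and leaves no interpretable group difference.
- If the Appendix 1 items are left out, the gap w × p stays in the coefficient.

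Neither reading gives a usable comparison. Descriptive group means of the full index carry the gap under both.

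**The case against.** The strongest reply is that the document never says Appendix 1 is the scoring list. The appendix gives no weights and does not mention the CCI. Sections 6.2 and 7.3.2 cite it for data collection and as covariates, and AIDS has a legitimate use there as a candidate risk factor within people with HIV. This stands in part: that AIDS enters the score is an inference. It is a reasonable one, because the indices are named without modification, no other comorbidity data are collected, and AIDS is among the items.

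A second reply is that AIDS is a real illness, so an index of total burden may properly count it. That is a fair definition for describing people with HIV. It does not support a comparison with people who are ineligible to have the condition. CDC stage and CD4 nadir are collected separately (section 6.2), so leaving the item out of the compared index loses no information. Section 7.3.1 reports frequencies of all categorical variables, so a careful reader could see how common AIDS was, but the regression estimate would still include it.

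Three stronger readings are tempting and are not supported:

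- A reader might infer that the outcome contains the exposure outright. The exposure is HIV infection, whereas AIDS applies to only some of those infected; if no case has AIDS, the gap is zero.
- A reader might infer that the gap will readily reach significance. At weight 1 and a 10% share the chance is 16%.
- A reader might extend the point to the VACO 30-day mortality index. The document does not give that index's composition, so nothing can be said about it.

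**Conclusion.** The point holds as a defect in one secondary endpoint. If the AIDS item is scored, as the plan's wording implies, the comparison carries a gap that can only run towards more comorbidity in people with HIV, and it is present whenever any case has AIDS. The direction follows from eligibility. The size does not: 0.05 to 1.8 points, with a chance of significance from 7% to near-certainty at SD 2, rests wholly on assumed weight, share and SD, and on a normal approximation that ignores the matching.

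Adjustment as written does not rescue the comparison, because it either leaves the gap in place or removes most of the index with it. The primary endpoint and the power figures in Table 1 are unaffected.

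**What to change.** In sections 3.4 and 7.3.3, specify that CCI and ACCI are computed without the AIDS item in both groups for the comparison of people with HIV and HIV-negative patients. Report the full index descriptively. State which Appendix 1 items are scored and with what weights, and define the AIDS item.

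In section 7.3.3, list the covariates for these two models. Leave out the Appendix 1 items that make up the index and, for ACCI, leave out age, which that index already contains.

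The cost is a few lines of SAP wording and a minor programming change, with no new data. The one downside is that the compared index is no longer the standard full CCI, so it is less directly comparable with published values; the descriptive full index partly offsets this.
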